Evaluation of pharmacist interventions in lipid management for secondary prevention

NCT06647238

Document date: October 24, 2024

Lipids Research Protocol

Title: Second Time's the Charm: Evaluation of pharmacist interventions in lipid management for secondary prevention

Principal Investigator: [name], BCACP, CDCES, CPP

Co-Investigators:

[name], MSCR

[name], CDCES, BCPS, CPP, DPLA

[name], CDCES, BCPS, CPP

[name], PharmD

[name], BCACP, CDCES, CPP

[name], BCPS, CPP, CDCES

Background/Significance:

Studies have shown prevention of cardiovascular adverse events is directly proportional to percent reduction in LDL.¹ This evidence explains why LDL targets for secondary prevention have continued to be lowered. Cholesterol guidelines have been updated recently and encourage the use of multiple lipid lowering therapies, in addition to statins, for secondary prevention. However, these novel agents can be expensive and difficult to acquire, making prescribing challenging for providers.

This project aims to utilize a pharmacist to evaluate patients for evidence-based therapy and initiate guideline-directed lipid lowering therapy as indicated.

Study Purpose:

The primary objective of this research project is to compare the effect of pharmacist interventions versus usual care in the implementation of guideline directed lipid lowering therapies for secondary prevention.

Study Design: prospective interventional study

Methods/Data Collection

Patient Identification:

- Internal medicine providers and PharmDs will identify patients who are not meeting LDL goals for secondary prevention and could benefit from pharmacist intervention
- SlicerDicer will be utilized to select patients for the control arm as well as potentially for the intervention arm if referrals alone do not meet the sample size goal

Collected data will be stored on a secure Atrium server and de-identified. Data will be analyzed utilizing REDCap. Data collected via EPIC may include:

- Demographic information (age, gender, race)
- Baseline information (recent lipid panel, Lp(a) history)
- Initial hyperlipidemia treatment
- Relevant lab information (renal function, electrolyte values)
- Other co-morbidities (diabetes, CKD, etc)
- Insurance type
- Follow up appointments
- Other relevant patient information for an appropriate hyperlipidemia treatment recommendation

The study period is expected to be 5 months (anticipated November 2024-March 2025).

Inclusion Criteria:

- Age \geq 18 yo

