PharmD services that are already in place at each practice. Adjustments to medication regimens, comorbidities, and concurrent medications will be made based on national guidelines and evidence-based recommendations that are already allowable by CPP and per our collaborative practice agreement. Any costs/risk associated with medication changes is no additional risk than if they do not participate in the study and would still be subject to these medication changes if they weren't participating in the study. This study and applicable additional intervention are simply offering additional care services provided by a PharmD for closer follow up and offering patients assistance with access to newer therapeutic options.

Control Group:

Patients meeting inclusion criteria will be pulled from SlicerDicer. Any patients previously referred to the project by their provider will be excluded from the control group. Patients included in the report will then be randomized and chosen for retrospective chart review. The goal will be to include 75 patients in both the intervention and control arms. Investigators will perform retrospective chart review for the study period and record the same data as collected for patients in the intervention arm.

Primary endpoint: patients with LDL within goal (<55) (yes/no)

Secondary endpoints:

- Percent LDL reduction (will use baseline LDL and lowest LDL)
- Medication related problems identified and solved
- Medications initiated or titrated
- Number of patients who were provided assistance with access to medication
- Prevalence of elevated Lp(a)

Data and Safety Monitoring:

Principal investigator and co-investigators will meet monthly to re-evaluate patient enrollment and ensure all investigators are adhering to study protocol.

Statistical Analysis:

Data will be analyzed after de-identification using descriptive statistics or inferential statistics as appropriate and will be collected, organized, and stored through REDcap. T-test will be utilized to compare pharmacist intervention versus usual care on the primary outcome. Descriptive statistics will be utilized to report secondary outcomes.

Feasibility of Project:

The anticipated start date for patient enrollment is November 2024. Statistical analysis will be finalized by April 2025. Anticipate presentations/publication in May or June 2025.

Informed Consent:

Participants will be required to provide signed informed consent prior to inclusion in the study.

References:

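### Percent LDL reduction, which the Background ties to cardiovascular benefit, has no planned between-arm estimate; the only comparison is LDL <55 yes/no, which discards much of the LDL information

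*Combined protocol and SAP*

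**What the plan says.** Background/Significance states that "prevention of cardiovascular adverse events is directly proportional to percent reduction in LDL", and adds that "This evidence explains why LDL targets for secondary prevention have continued to be lowered".

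The main outcome is binary: "Primary endpoint: patients with LDL within goal (<55) (yes/no". The first secondary endpoint is continuous: "Percent LDL reduction (will use baseline LDL and lowest LDL".

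Statistical Analysis opens with a general sentence about "using descriptive statistics or inferential statistics as appropriate". It then gives two specific instructions: "T-test will be utilized to compare pharmacist intervention versus usual care on the primary outcome", and "Descriptive statistics will be utilized to report secondary outcomes". No other between-arm comparison is assigned to any endpoint. The Control Group section sets a target of 75 patients in each arm and has the same data recorded for controls by chart review.

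**The concern.** The study sets out to compare pharmacist intervention with usual care. On the quantity that its own rationale names, it specifies no between-arm difference, standard error or confidence interval.

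The one planned comparison reduces LDL to a cut at 55. A patient who goes from 140 to 58 counts the same as one who does not change, and a patient who goes from 56 to 54 counts as a full success. The study could lower LDL by a relevant amount, report a non-significant primary result, and have no prespecified estimate of the LDL effect to set beside it. A comparison added later would be open to the suspicion that it was chosen after the data were seen.

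**Working it through.** **Inputs from the documents.** 75 per arm (Control Group); entry LDL above 55, so everyone starts on the wrong side of the cut (Inclusion Criteria); a 5-month study period.

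**Not in the documents.** Alpha, power, effect size, SD, goal rates and dropout. The figure of 75 therefore cannot be reproduced. Assumed below: two-sided 5%, LDL in mg/dL, and the ranges shown.

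**1. Information kept by a yes/no cut.** For a normal outcome and a small shift, the fraction kept is φ(c)²/[p(1−p)], where p is the proportion at goal and c = z(p). At p = 0.20, φ(c) = 0.280 and 0.280²/0.16 = 0.49.

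| At goal | 50% | 30% | 20% | 10% | 5% |
|---|---|---|---|---|---|
| Kept | 64% | 58% | 49% | 34% | 22% |

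Against an unadjusted continuous comparison the loss is thus 36% to 78%, and it passes one half only below about 21% at goal. Baseline adjustment at an assumed correlation of 0.5 multiplies the continuous variance by 1 − 0.5² = 0.75. Even the best case for the cut then becomes 0.64 × 0.75 = 0.48.

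**2. Power for the same shift.** Put d = z(pt) − z(pc), with pc and pt the control and intervention goal rates. For 10% versus 25%:
- Continuous: d = 1.282 − 0.674 = 0.608. Then 0.608/√(2/75) − 1.96 = 1.76, and power is 96%.
- Yes/no: the pooled rate is 0.175. The standard errors are √(2 × 0.175 × 0.825/75) = 0.0620 under the null and √((0.10 × 0.90 + 0.25 × 0.75)/75) = 0.0608 under the alternative. (0.15 − 1.96 × 0.0620)/0.0608 = 0.47, and power is 68%.

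| At goal, control vs intervention | Yes/no | Continuous, unadjusted |
|---|---|---|
| 10% vs 20% | 40% | 77% |
| 10% vs 25% | 68% | 96% |
| 20% vs 35% | 54% | 80% |
| 30% vs 45% | 48% | 69% |

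**3. Simulation with a shared effect.** 75 per arm, 2,000 trials per scenario. Baseline LDL is log-normal with log-SD 0.30, truncated above 55. Baseline/follow-up correlation is 0.4 to 0.8. Every patient is measured, and every intervention patient has the same percent lowering. The t-test on yes/no is set against linear regression of log follow-up LDL on arm and log baseline LDL.

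| Median baseline, lowering | Yes/no | Regression on log LDL |
|---|---|---|
| 85, 10% | 24-27% | 62-94% |
| 85, 15% | 51-58% | 95% to >99% |
| 85, 20% | 81-88% | about 100% |
| 95, 15% | 35-38% | 95% to >99% |

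In the 85, 15% row the goal rates are about 4-6% versus 13-16%.

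**4. Simulation with a concentrated effect.** Now 20% of intervention patients have a 50% fall and the rest do not change. Yes/no power is 77-89% and regression power is 69-90%. If the follow-up spread is scaled to the truncated baseline, the figures are 89-92% and 75-94%. The advantage seen in step 3 is gone, and at the lower correlations it reverses.

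**5. What an interval would show.** For an unadjusted difference in percent LDL reduction, the 95% half-width is 1.96 × SD × √(2/75) = 0.32 × SD. That is 6.4 points at an assumed SD of 20 and 11.2 at 35.

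**6. The lowest-LDL definition.** With no true change, the expected minimum of 2 normal values lies 0.564 SD below the mean, and of 3 values 0.846 SD below. With an assumed within-person CV of 7-15%, the apparent reduction is 0.564 × 7 = 3.9 to 0.564 × 15 = 8.5 points for 2 values, and 0.846 × 7 = 5.9 to 0.846 × 15 = 12.7 for 3. For a single value it is 0. Intervention patients have a panel before each follow-up visit, while controls have only what their charts hold.

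**The case against.** Reporting secondary endpoints descriptively is permissible, and it avoids multiplicity claims in a small study without randomised arms. The general sentence leaves some room for inference, and published means and SDs would let a reader compute an unadjusted interval. The goal-based endpoint has its own rationale, because the Background uses the same evidence to explain falling LDL targets. The plan also describes treatment adjusted patient by patient, with pharmacist follow-up ending once LDL is below 55, and help with access to newer agents. A few large falls are therefore as plausible as a uniform shift, and step 4 shows that the power argument then fails. Some controls may have no LDL in the study period. Finally, a narrow interval does nothing about confounding between mainly referred patients and a chart-review sample.

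Most of this stands, and it limits the point. It does not close the gap. The general sentence assigns no method to percent LDL reduction, and the later, specific sentence makes it descriptive. An interval that a reader might rebuild would be neither baseline-adjusted nor free of the lowest-value problem.

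A reader might go further and infer that the cut discards most of the LDL information. The documents give no goal rates or SD to support that. Low attainment is plausible because everyone enters above 55, but it is not stated. A reader might also infer that a continuous analysis is more powerful whatever the effect, or that the yes/no endpoint is the wrong primary. Step 4 contradicts the first, and the Background's link to targets answers the second.

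**Conclusion.** The point holds in a limited form. On the text alone, the only specified between-arm inference is on LDL <55, and the outcome tied to benefit has no specified effect estimate or interval. That needs no assumption.

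The cost in information is substantial but conditional: 36% to 78% against an unadjusted continuous comparison, for 50% down to 5% at goal. The power gap of about 51-58% versus 95% or more assumes a 15% lowering shared by all patients, median baseline 85 and complete LDL. With a few large responders there is no consistent gap. Nothing in the plan is invalidated, but the change is worth making before analysis.

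**What to change.** Keep LDL <55 as the primary endpoint. In Statistical Analysis, replace the descriptive-only sentence, as it applies to percent LDL reduction, with wording such as:

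> The between-arm difference in LDL will be estimated by linear regression of log follow-up LDL on arm and log baseline LDL, and reported as a percent difference with 95% CI. One follow-up LDL per patient will be used, chosen by the same rule in both arms (for example, the last value in the study period). The number of patients with a follow-up LDL will be given for each arm. This is a secondary estimate, with no multiplicity claim, and is open to confounding from referral versus chart-review selection.

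Change the endpoint definition under Secondary endpoints to match, so that the lowest LDL is no longer used. The plan does not say which LDL decides the primary endpoint either, so the same rule could serve both.

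The cost is one more regression and one more interval, on LDL values that the plan already has recorded. Patients without a follow-up LDL do not contribute, so fewer than 75 per arm may be analysed. A last-value rule is also not fully neutral, because pharmacist follow-up ends once LDL is below 55; a value nearest a fixed date would be less exposed to this. Baseline adjustment deals only with imbalance in baseline LDL.
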